8.2.2 Clinical laboratory tests

The following clinical laboratory tests will be performed at each study site with reference range for each test provided (see the Schedule of Assessments, Appendix C and Appendix D for the timepoints of each test):

- Hematology (Table 6)
- Clinical Chemistry (Table 7)
- Coagulation parameters: Activated partial thromboplastin time and International normalised ratio to be assessed at baseline and as clinically indicated
- Urine analysis (Table 8)
- Urine cytology with Urovysion FISH test
- Thyroid Stimulating Hormone
 - free T3 and free T4 only if TSH is abnormal
- Pregnancy test (female subjects of childbearing potential only)
 - Urine human chorionic gonadotropin
 - Serum beta-human chorionic gonadotropin (at screening only)
- Other laboratory tests
 - Hepatitis B surface antigen, hepatitis C antibody
 - HIV antibody

Clinical Study Protocol

Drug Substance Durvalumab (Medi4736)

Study Number MCC 18788/MCC18788/ESR-15-11326

Edition Number 1.9.4

Date 10/08/2018

Table 6. Hematology Laboratory Tests

Basophils	Mean corpuscular volume
Eosinophils	Monocytes
Hematocrit	Neutrophils
Hemoglobin	Platelet count
Lymphocytes	Red blood cell count
Mean corpuscular hemoglobin	Total white cell count
Mean corpuscular hemoglobin concentration	

Table 7. Clinical chemistry (Serum or Plasma) Laboratory Tests

Albumin	Glucose
Alkaline phosphatase	Lactate dehydrogenase
Alanine aminotransferase	Lipase
Amylase	Magnesium
Aspartate aminotransferase	Potassium
Bicarbonate	Sodium
Calcium	Total bilirubin ^a
Chloride	Total protein
Creatinine	Urea or blood urea nitrogen, depending on local practice
Gamma glutamyltransferase ^b	Uric acid

^a If Total bilirubin is $\geq 2 \times \text{ULN}$ (and no evidence of Gilbert's syndrome) then fractionate into direct and indirect bilirubin

^b At baseline and as clinically indicated

Table 8. Urinalysis Tests^a

Bilirubin	pH
Blood	Protein
Glucose	Specific gravity
Ketones	Colour and appearance

^a Microscopy should be used as appropriate to investigate white blood cells and use the high power field for red blood cells

8.3 Biological sampling procedures for PD-L1 testing

To ensure comparability of data across all studies of durvalumab, the Ventana SP263 assay will be used for testing PD-L1 expression. Testing should be restricted to the Ventana SP263 assay and should be performed in accordance with the package insert on the Ventana Benchmark platform (Ultra or XT).

The Ventana SP263 assay is fully analytically validated test characterized through to the completion of reader precision studies in the non-small cell lung cancer (NSCLC) and squamous cell carcinoma of the head & neck (SCCHN). For these tumors, the Ventana SP263 assay has a fully reproducibility data package supporting cut-off and scoring algorithm. Following completion of ATLANTIC and HAWK clinical trials, the assay will be associated with clinical utility. In other cancer types (bladder, pancreatic, gastric, hepatocellular, triple negative breast, ovarian, esophageal, nasopharyngeal, glioblastoma, soft tissue sarcoma, cholangiocarcinoma, small cell lung, melanoma and cervical HPV+ cancers), the Ventana SP263 assay has only limited clinical performance data.

Sample collection for PD-L1 testing

- The preferred tumor sample for the determination of a patient's PD-L1 status is the one taken following the completion of the most recent prior line of therapy. Samples taken at this time reflect the current PD-L1 status of the tumor and considered clinically most relevant.
- The preferred bladder biopsies or TURBT sample for PD-L1 testing was less than or equal to 90 days old. In cases where a sample of less than 90 days old was not available, patients were asked to undergo a new cystoscopic bladder biopsy and or TURBT.
- Samples should be evaluated for tumor cell quantity (i.e. >100 tumor cells) to allow for adequate PD-L1 immunohistochemistry analyses.
- When the collection of a new CIS sample with adequate tumor cell quantity is not clinically feasible, archival samples may be utilized provided the specimen it is not

older than 3 years of age. When archival samples are used to assess PD-L1 status, the age of the sample / date of collection should be captured.

- Samples submitted for PD-L1 testing should be formalin fixed and embedded in paraffin.

Sample data collection for PD-L1 testing

The following fields of data should be collected from the site/institution collecting and if, indicated shipping of the samples:

- Patient identifier (ecode or unique identifier)
- Specimen identifier (written on the specimen)
- Site identifier
- Specimen collection date
- Type of specimen submitted
- Quantity of specimen
- Date of sectioning
- Archival of fresh tumor
- Tumor type
- Primary tumor location
- Metastatic tumor location (if applicable)
- Fixative

The following fields of data should be collected from PD-L1 testing laboratory:

- Are the negative and positive controls stained correctly
- Is the H&E material acceptable
- Is morphology acceptable
- Total percent positivity of PD-L1 in tumor cells
- PD-L1 status (positive, negative or NA) in tumor cells
- Total percent positivity of PD-L1 in infiltrating immune cells

The Ventana SP263 assay to measure PD-L1 in tumors is experimental. As with all tests, there is a chance of false positive (the test shows high PD-L1 when it is not there) or false negative (the test does not show PD-L1 when it is there) results may occur.

Sample processing and if indicated submission process for PD-L1 testing

Preparing Stored samples for testing

- Where samples already exist, they should be retrieved from the Bio-Bank storage location. These blocks should undergo quality review, prior to evaluation or shipment. Where it is not possible or indicated to ship the block to a testing laboratory, unstained slides should be prepared from the paraffin-embedded tumor sample block (described below) prior to evaluation or shipment.

Preparing newly acquired samples for PD-L1 testing

- If patients are undergoing a biopsy procedure that provides the option to submit newly acquired samples, this sample should be used to determine PD-L1 status. Where clinically acceptable, a minimum of 2 core biopsies should be collected and processed to FFPE in a single block. The provision of 2 cores is advised in order to provide sufficient tissue for PD-L1 assessment.
- Samples should be evaluated for tumor cell quantity (i.e. >100 tumor cells) and embedded in the same block.

Fixation of biopsy samples for PD-L1 testing

- Previously frozen tissue is not acceptable for processing to FFPE for PD-L1 testing. To fix newly acquired tissue, place immediately (within 30 min of excision) into an adequate volume of 10% v/v neutral buffered formalin (NBF). Samples should remain in fixative for 24 – 48 hours at room temperature.
- It is vital that there is an adequate volume of fixative relevant to the tissue (at least a 10 volume excess) and that large specimens (if any) are incised prior to fixation to promote efficient tissue preservation.

Embedding in paraffin for PD-L1 testing

- An overnight processing schedule into paraffin wax is recommended
- Below is the suggested routine overnight processing schedule:

Storage of tumor blocks for PD-L1 testing

- FFPE blocks should be stored at ambient temperature and protected from light until shipment by courier at ambient temperature. FFPE blocks are stable under these conditions for an indefinite period.

Quality control of samples to be used for PD-L1 testing

- Tissue should be assessed by the site pathologist prior to PD-L1 testing.
- Each sample should be reviewed for:
 - Adequate fixation
 - Good preservation of morphology
 - Presence of tumor tissue
 - Histopathology consistent with indication
 - Greater than 100 tumor cells are required to determine PD-L1 status – tumor cell content must be reviewed prior to testing in order for PD-L1 obtain a valid result.

If indicated, shipping samples to a PD-L1 testing laboratory

- When submitting sample to for PD-L1 testing the recommendation is to ship the block in order for sectioning to occur at the laboratory. Blocks should be shipped - containing enough material to be provided to allow a minimum of 5, and preferably 10, sections to be cut (each 4 micron thick) to be used for PD-L1 testing.

Sectioning instructions

- Where it is not possible or indicated to ship the block to laboratory for PD-L1 testing, unstained slides should be prepared from the paraffin-embedded tumor sample block as described below:
 - A minimum of 5-10 x 4 micron (μ m) thick, unstained sections should be provided for PD-L1 testing
 - A new disposable microtome blade must be used for each block to prevent contamination between Slides are stable under these conditions for 6 months.
 - patient samples
 - Apply one section per slide to positively-charged Superfrost glass slides
 - The sections should be dried overnight between room temperature and 37°C. Do not dry sections at temperatures above 37°C.

Clinical Study Protocol

Drug Substance Durvalumab (Medi4736)

Study Number MCC 18788/MCC18788/ESR-15-11326

Edition Number 1.9.4

Date 10/08/2018

Sections should be stored at ambient temperature and protected from light until use or shipment to testing lab by courier at ambient temperature. It is recommended that slides are cut freshly prior to PD-L1 testing and they are used within 90 days of being cut to obtain PD-L1 status.

9. DISEASE EVALUATION AND METHODS

The response to immunotherapy may differ from the typical responses observed with cytotoxic chemotherapy including the following (Wolchok et al 2009, Nishino et al 2013):

- Response to immunotherapy may be delayed
- Response to immunotherapy may occur after PD by conventional criteria
- The appearance of new lesions may not represent PD with immunotherapy
- SD while on immunotherapy may be durable and represent clinical benefit.

Based on the above-described unique response to immunotherapy, subjects with persistent CIS at the month 3 bladder biopsy will continue to receive Durvalumab until the month 6 bladder biopsy documented persistent CIS or progression to the muscle invasive stage. Durvalumab will be discontinued and subjects will be off study if invasive bladder cancer (T1 or above) is documented in any of the bladder biopsies. Due to the nature of CIS of bladder, RECIST 1.1 or irRECIST will not be applicable to response assessment.

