- Compare the tumor mutation burden and alterations in DNA repair genes in the pre and post Durvalumab urothelial bladder cancer samples

Study Design:

This is a multicenter, open-label, Phase 2 study of Durvalumab to evaluate its antitumor activity for BCG refractory urothelial carcinoma in situ (CIS) of the bladder. Durvalumab will be given every 4 weeks at 1500 mg IV for total of 12 months. Cystoscopy with biopsy and TURBT (if indicated) will be performed at baseline, and every 3 months during the 12 months treatment period and then every 4 months in the 12 month surveillance period. Of note, cystoscopy at baseline, month 6, and 24 will be performed in the operating room with mapping biopsies. Patients will be off study if any of the biopsies document muscle invasive (T2 or above) urothelial carcinoma. Patients will also be off study if their month 6, 12, 16, 20, biopsies show persistent (month 6) or recurrent CIS or invasive (T1 or above) urothelial carcinoma. Otherwise, patients will remain on study until after the month 24 biopsy.

Number of Centers: 2-3 centers in North America

Number of Subjects: 34

Study Population:

Adult male or female subjects with pathologically confirmed urothelial carcinoma in situ (CIS) of the bladder that is refractory to BCG (see inclusion criteria 2).

Inclusion Criteria:

1. Age \geq 18 years at the time of screening with life expectancy of \geq 2 years
2. Must have pathologically confirmed urothelial carcinoma in situ (CIS) of the bladder that meet one of the following criteria:
 1. Persistence of high-grade CIS at 6 months following an adequate course of BCG; OR
 2. Stage/grade progression at 3 months after induction BCG; OR
 3. Recurrence of high-grade CIS after achieving a disease-free state (i.e., CR) following induction of an adequate course of BCG that occurs $<$ 9 months after the last exposure to BCG; OR
 4. Persistent CIS noted on the bladder biopsies within 3 months of completing at least 2 induction BCG (minimum of five weekly instillations).
- An adequate course of BCG should be defined as at least one course of induction (minimum of five weekly instillations) and one maintenance (two of three instillations) in a 6 months period, with an exception for any patient with grade/stage progression after induction BCG (minimum of five weekly instillations).
3. ECOG performance status of 0-1.

4. Adequate organ and marrow function, as defined as:

- Hemoglobin ≥ 9.0 g/dL,

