3. STUDY DESIGN

3.1 Overview of study design

This is a multicenter, open-label, Phase 2 study of Durvalumab to evaluate its antitumor activity for BCG refractory urothelial carcinoma in situ (CIS) of the bladder. We use a Simon's two-stage design (Simon, 1989) based on the optimal two-stage designs and admissible designs (Jung et al. 2004) for Phase II single arm clinical trials. In the first stage of this study plan, 13 patients will be accrued. If there are 3 or fewer responses in these 13 patients, the study will be stopped. Otherwise, 21 additional patients will be accrued for a total of 34. Durvalumab will be given every 4 weeks at 1500 mg IV for total of 12 months/13 doses. Cystoscopy with mapping biopsy and TURBT (if indicated) will be performed at

Clinical Study Protocol

Investigational Drug Substance: MEDI4736 Durvalumab (Medi4736)

Study Number MCC 18788/MCC18788/ESR-15-11326

Edition Number 1.9.4

Date 10/08/2018

baseline, month 6, and 24. Urine cytology with UroVysion test will be performed at baseline, month 6, and 24. Patients will be off study if any of the biopsies documented muscle invasive (T2 or above) urothelial carcinoma. Patients will also be off study if their month 6, 12, 18 biopsies showed persistent (month 6) or recurrent CIS or invasive (T1 or above) urothelial carcinoma. Otherwise, patient will remain on study until after the month 24 biopsy.

Historical controls will be used to assess the efficacy of Durvalumab. For exploratory analysis on PD-L1 expression, PD-L1 IHC will be performed with the SP263 antibody developed by Ventana. IHC positivity (either on tumor cells and/or infiltrating immune cells) will be assessed on the available mapping biopsy and or TURBT samples at time points defined in SCHEDULE OF STUDY ASSESSMENT.

Data Monitoring Committee (DMC) at Moffitt Cancer Center will monitor this phase 2 study initiated by Moffitt's investigator.

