4.4 Replacement of subjects

Subjects withdrawn from the study prior to the month 6 /week 26 mapping biopsy will be replaced to ensure total of 34 evaluable subjects. Subjects who are incorrectly enrolled but are not yet initiated on treatment should be withdrawn from the study and replaced.

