9.1.1 Pathological response

The absence of CIS of bladder on the mapping biopsies after pathological review would be considered complete response to treatment. Subjects who are withdrawn from durvalumab treatment for reasons other than confirmed progression to the muscle invasive stage will continue to have objective tumor assessments (see Appendix C).

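### Complete response is defined by absence of CIS alone, so T1 without CIS at week 26 counts as a response; T1 at month 3 falls under conflicting off-study rules that can remove a failure from the count.

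*Combined protocol and SAP*

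**What the plan says.** **Response definition.** Section 9.1.1: "The absence of CIS of bladder on the mapping biopsies after pathological review would be considered complete response to treatment". Section 9.1.2 adds that the primary and secondary objectives rest on pathological response alone. T1 disease is not mentioned in either place.

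**Off-study rules for T1.**
- Section 9, at any biopsy: "subjects will be off study if invasive bladder cancer (T1 or above) is documented in any of the bladder biopsies".
- Section 9, preceding sentence: patients with CIS at month 3 stay on durvalumab "until the month 6 bladder biopsy documented persistent CIS or progression to the muscle invasive stage".
- Synopsis, Study Design, at any biopsy: "Patients will be off study if any of the biopsies document muscle invasive (T2 or above) urothelial carcinoma". T1 is a reason to leave only if the "month 6, 12, 16, 20, biopsies show persistent (month 6) or recurrent CIS or invasive (T1 or above) urothelial carcinoma".
- Section 3.1: the same structure, but the list reads "month 6, 12, 18 biopsies showed persistent (month 6) or recurrent CIS or invasive (T1 or above) urothelial carcinoma".

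**Counting rules.** Section 4.4: "Subjects withdrawn from the study prior to the month 6 /week 26 mapping biopsy will be replaced to ensure total of 34 evaluable subjects". Section 6.1 repeats this and makes six doses a condition of being evaluable. Section 11.1.2 requires the month 6 mapping biopsy in both analysis sets: six doses for the efficacy set, one dose for the set called intention to treat. The stage 1 look in the interim analysis section is taken on 13 patients who have had the month 6 biopsy.

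**Biopsy timing.** Under footnote j of the schedule, the week 26 and week 104 mapping biopsies are fixed, while a month 3 biopsy is at the urologist's discretion.

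**The concern.** Two separate gaps affect the primary count.

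First, the response definition covers one lesion type. T1 is foreseeable here: Section 4.2 excludes only T2 or above, and the synopsis safety paragraph expects some stage I patients with a CIS component. At week 26 the same biopsy can be both the reason a patient leaves the study for invasive cancer and a complete response. The definition also governs the year 2 endpoint at week 104.

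Second, T1 at month 3 means off study under Section 9 but not under the synopsis or 3.1. If Section 9 is followed and the exit is treated as a withdrawal, a treatment failure is replaced and leaves both the numerator and the denominator.

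The cut-offs are 4 of 13 and 10 of 34, so the handling of a single patient can change the decision.

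**Working it through.** **Step 1. Set the rules side by side for T1 or above (not T2).**

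| Finding | Synopsis | 3.1 | Section 9 | 9.1.1 |
|---|---|---|---|---|
| T1 at month 3 | not listed | not listed | off study | not addressed |
| T1 without CIS at week 26 | off study | off study | off study | complete response |

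The second row is the endpoint gap and needs no assumption about patient handling. The first row is the management conflict.

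**Step 2. Follow T1 at month 3 into the count.**
- (a) Off study and treated as withdrawn: replaced under 4.4 and 6.1, absent from both sets in 11.1.2 and from the 13-patient look.
- (b) Drug stopped but week 26 biopsied: doses at weeks 0, 4, 8 and 12 make 4, or 5 if the month 3 biopsy falls late in its +14 day window (week 14 + 2 = 16). That is below six, so the patient is outside the efficacy set and appears only in the one-dose set. CIS at week 26 is a failure there; T1 alone is not.
- (c) Kept on drug: the week 26 biopsy decides. CIS is a failure; T1 alone is not, under the present 9.1.1.

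**Step 3. Reproduce the design.** Inputs from 11.2 and 11.3: 13 then 21 patients, at least 4 responses to continue and at least 10 of 34 to pass. Exact formula:

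P(pass | p) = sum over x = 4 to 13 of Bin(x; 13, p) × P[Bin(21, p) ≥ 10 − x].

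At p = 0.18 this gives 0.0473, and at p = 0.40 it gives 0.8031. Both match the plan's table.

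**Step 4. One T1 patient in 34, with 18% the true response rate among all treated patients.** The other 33 then respond at 0.18 × 34/33 = 0.1855. The T1 patient falls in stage 1 with probability 13/34 and in stage 2 with probability 21/34.
- Counted as failure: 13/34 × 0.0430 + 21/34 × 0.0492 = 0.047.
- Replaced (all 34 at 0.1855): 0.056.
- Scored complete response: 13/34 × 0.1135 + 21/34 × 0.0862 = 0.097.

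**Step 5. Replacement over an assumed range of T1 exits.** Let a fraction f of enrolled patients, none of them responders, be removed and replaced. The rate becomes 0.18/(1 − f).
- f = 3%: 0.1856, chance of passing 0.056.
- f = 5%: 0.1895, 0.063.
- f = 10%: 0.2000, 0.084.

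**Step 6. Literal 9.1.1 over an assumed range.** Let a fraction t have T1 without CIS at week 26, on top of an 18% disease-free rate. At t = 3% the rate is 0.21 and the chance of passing 0.108; at t = 5%, 0.23 and 0.167.

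Both f and t are assumptions; the documents give neither.

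**The case against.** **No one would score T1 as a complete response.** Three places remove that patient for invasive cancer at the same biopsy, so failure may seem implied. Nothing shows that scoring it as a response is intended, and a reader should not infer that. But those rules govern participation, and the only response definition names CIS alone. The gap stands.

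**A month 3 T1 patient need not be lost.** Section 9.1.1 says "Subjects who are withdrawn from durvalumab treatment for reasons other than confirmed progression to the muscle invasive stage will continue to have objective tumor assessments", and 6.1 follows patients with fewer than six doses through month 24. Such a patient could reach the week 26 biopsy and the one-dose set. This stands: replacement is one possible handling, and the protocol does not say whether it applies.

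**Section 9 can be read consistently.** Its T1 sentence can be taken to override the preceding one on CIS at month 3. That is fair; the firm conflict is with the synopsis and 3.1.

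**T1 at month 3 is not failure at month 6.** The endpoint is the week 26 biopsy, resection is allowed, and Section 9 expects delayed responses. A patient kept on drug and clear of CIS and T1 at week 26 is a legitimate responder. This also stands, so it would be too strong to make every month 3 T1 a permanent non-response.

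**The effect may be very small.** The month 3 biopsy is discretionary and no T1 rate is given. True; it could be about one patient. That excuses neither the week 26 gap, where biopsy is fixed, nor the conflicting instructions.

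**Conclusion.** The point holds as a defect in the response definition plus a conflict in the T1 off-study rule, and should be fixed. The text supports both with high confidence. The effect on the primary result is uncertain.

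Two stronger conclusions are tempting and are not supported:
- That every route raises the observed response rate. CIS at week 26 still counts as a failure when the patient stays on drug, and in the one-dose set when drug was stopped. Only the branches in which T1 alone is scored a response, or a T1 exit is replaced or left out of the efficacy set, can raise it.
- That the trial's type I error exceeds its nominal level. The 18% is a 3-month figure in Section 1.1. If the true month 6 null rate were 15% (an assumption), the chance of passing would be 0.015, rising to 0.019 with 3% of patients replaced and 0.030 with 10%.

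The 0.047, 0.056 and 0.097 show the leverage of one patient under three handlings. The 0.097 takes one such case as certain and is not an expected value. The replacement effect comes from general rules that touch other early exits too; only T1 is counted here.

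**What to change.** 1. In 9.1.1, require absence of both CIS and invasive (T1 or above) urothelial carcinoma on the mapping biopsies for complete response, at week 26 and week 104.
2. Use one T1 off-study rule in the synopsis, 3.1 and Section 9. Whether T1 at month 3 ends treatment is the investigators' clinical choice.
3. In 4.4, 6.1 and 11.1.2, state that a patient taken off drug or off study for T1 or above at or before week 26 is a non-responder, stays in the denominator and is not replaced. Apply the same count at the 13-patient look.
4. If the investigators keep month 3 T1 patients on drug, let the week 26 biopsy decide their response under the corrected 9.1.1.

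**Cost.** A wording amendment, with no added visits, procedures or patients. The observed response rate may be slightly lower, and some power is lost if some of those removed would have been clear at week 26. As an upper illustration, suppose 3% to 10% are removed and would otherwise have responded at 40%. The true rate falls to 0.40 × 0.97 = 0.388 or 0.40 × 0.90 = 0.360, and power from 0.803 to 0.772 or 0.686. This is the opposite assumption from the replacement figures, where none of those removed would have responded, so the two sets of numbers should not be netted against each other.
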